13.3 Derived Efficacy and Safety Variables

The total score of each variable including MADRS, [REDACTED] at a particular visit will be calculated using $(\text{sum of nonmissing items}) \times (\text{total number of items}) / (\text{number of non-missing items})$ only if the number of missing items is less than the specified number for each variable. Otherwise, the total score will be set to missing.

Specifically, if more than 2 items are missing for MADRS, then the total score will be set to missing; [REDACTED]

Derivation of S-STS total score is detailed in [Appendix II](#).

13.4 Repeated or Unscheduled Assessments of Safety Parameters

If a patient has repeated assessments before the start of the first treatment, the results from the last non-missing assessment made prior to the start of the IP will be used as baseline. If end-of-study assessments are repeated or if unscheduled visits occur, the last non-missing postbaseline assessment will be used as the end-of-study assessment for generating summary statistics. However, all postbaseline assessments will be used for PCS value determinations, and all assessments will be presented in the data listings.

13.5 Missing Severity Assessment for Adverse Events

If severity is missing for an AE that started before the date of the first dose of IP, an intensity of mild will be assigned. If severity is missing for an AE that started on or after the date of the first dose of IP, an intensity of severe will be assigned. The imputed values for severity assessment will be used for the incidence summary; the values will be shown as missing in the data listings.

13.6 Missing Causal Relationship to Study drug for Adverse Events

If the causal relationship to the IP is missing for an AE that started on or after the date of the first dose of IP, a causality of yes will be assigned. The imputed values for causal relationship to IP will be used for the incidence summary; the values will be shown as missing in the data listings.

13.7 Missing Date Information for Adverse Events

The following imputation rules only apply to cases in which the start date for AEs is incomplete (i.e., partly missing).

Missing month and day

- If the year of the incomplete start date is the same as the year of the first dose of IP, the month and day of the first dose of IP will be assigned to the missing fields.
- If the year of the incomplete start date is before the year of the first dose of IP, *December 31* will be assigned to the missing fields.
- If the year of the incomplete start date is after the year of the first dose of IP, *January 1* will be assigned to the missing fields.

Missing month only

- If only the month is missing, the day will be treated as missing and both the month and the day will be replaced according to the above procedure.

Missing day only

- If the month and year of the incomplete start date are the same as the month and year of the first dose of IP, the day of the first dose of IP will be assigned to the missing day.
- If either the year of the incomplete start date is before the year of the date of the first dose of IP or if both years are the same, but the month of the incomplete start date is before the month of the date of the first dose of IP, the last day of the month will be assigned to the missing day.
- If either the year of the incomplete start date is after the year of the date of the first dose of IP or if both years are the same, but the month of the incomplete start date is after the month of the date of the first dose of IP, the first day of the month will be assigned to the missing day.

If the stop date is complete and the imputed start date as above is after the stop date, the start date will be imputed by the stop date.

If the start date is completely missing and the stop date is complete, the following algorithm will be used to impute the start date:

- If the stop date is after the date of the first dose of IP, the date of the first dose of IP will be assigned to the missing start date.
- If the stop date is before the date of the first dose of IP, the stop date will be assigned to the missing start date.

13.8 Missing Date Information for Prior or Concomitant Medications

For prior or concomitant medications, including background ADT, incomplete (i.e., partially missing) start dates and/or stop dates will be imputed. When the start date and the stop date are both incomplete for a patient, the start date will be imputed first. If the stop date is complete and the imputed start date is after the stop date, the start date will be imputed using the stop date. If the imputed stop date is before the start date (imputed or non-imputed start date), the start date will be the imputed stop date.

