9.4.9 Prior and Concomitant Therapy

Medication history (psychotropic medication history during the previous 2 years and all other medications during the past 12 months) will be recorded at Screening (Visit 1) in the eCRF. Thereafter, any changes in concomitant medications or any new medications added will be recorded in the eCRF.

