7.0 DEMOGRAPHICS AND OTHER BASELINE CHARACTERISTICS

Demographic parameters (eg, age, race, ethnicity, sex, weight, height, body mass index) and other baseline characteristics will be summarized overall and by treatment group for the mITT Population.

Medical and surgical history, psychiatric history, previous treatment with psychotropic medication, and nondrug psychiatric treatment will be summarized by treatment group for the Safety Population.

Prior medication is defined as any medication taken before the date of the first dose of randomized IP. Concomitant medication is defined as any medication taken on or after the date of the first dose of randomized IP.

Both prior and concomitant medication use will be summarized by the number and proportion of patients in each treatment group receiving each medication within each therapeutic class for the Safety Population. Multiple medication use of the same therapeutic class by a patient will only be counted once.

The *World Health Organization (WHO) Drug Dictionary Enhanced* will be used to classify prior and concomitant medications by therapeutic class and drug name.

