13.8.1 Incomplete Start Date

The following rules will be applied to impute the missing numeric fields for an incomplete prior or concomitant medication start date.

Missing month and day

- If the year of the incomplete start date is the same as the year of the first dose of IP, the month and day of the first dose of IP will be assigned to the missing fields.
- If the year of the incomplete start date is before the year of the first dose of IP, *December 31* will be assigned to the missing fields.
- If the year of the incomplete start date is after the year of the first dose of IP, *January 1* will be assigned to the missing fields.

Missing month only

- If only the month is missing, the day will be treated as missing and both the month and the day will be replaced according to the above procedure.

Missing day only

- If the month and year of the incomplete start date are the same as the month and year of the first dose of IP, the day of the first dose of IP will be assigned to the missing day.
- If either the year of the incomplete start date is before the year of the date of the first dose of IP or if both years are the same, but the month of the incomplete start date is before the month of the date of the first dose of IP, the last day of the month will be assigned to the missing day.
- If either the year of the incomplete start date is after the year of the date of the first dose of IP or if both years are the same, but the month of the incomplete start date is after the month of the date of the first dose of IP, the first day of the month will be assigned to the missing day.

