13.8.2 Incomplete Stop Date

The following rules will be applied to impute the missing numeric fields for an incomplete prior or concomitant medication stop date. If the imputed stop date is before the start date (imputed or non-imputed start date), the imputed stop date will be equal to the start date.

Missing month and day

- If the year of the incomplete stop date is the same as the year of the last dose of IP, the month and day of the last dose of IP will be assigned to the missing fields.
- If the year of the incomplete stop date is before the year of the last dose of IP, *December 31* will be assigned to the missing fields.
- If the year of the incomplete stop date is after the year of the last dose of IP, *January 1* will be assigned to the missing fields.

Missing month only

- If only the month is missing, the day will be treated as missing and both the month and the day will be replaced according to the above procedure.

[figure not shown]
Missing day only

- If the month and year of the incomplete stop date are the same as the month and year of the last dose of IP, the day of the last dose of IP will be assigned to the missing day.

- If either the year of the incomplete stop date is before the year of the date of the last dose of IP or if both years are the same, but the month of the incomplete stop date is before the month of the date of the last dose of IP, the last day of the month will be assigned to the missing day.
- If either the year of the incomplete stop date is after the year of the date of the last dose of IP or if both years are the same, but the month of the incomplete stop date is after the month of the date of the last dose of IP, the first day of the month will be assigned to the missing day.

[REDACTED]

[REDACTED]

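### SAP 13.8 and 13.8.2 resolve the same medication-date conflict in opposite ways, which in one narrow pattern of partial dates can turn a prior drug into a concomitant one

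*SAP*

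**What the plan says.** SAP 13.8 sets the order of work: "When the start date and the stop date are both incomplete for a patient, the start date will be imputed first". It then gives a conflict rule for an imputed stop date that precedes the start date: "the start date will be the imputed stop date". The rule expressly covers a start date that was not imputed.

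SAP 13.8.2 opens with the same condition, including the same parenthesis, but concludes that "the imputed stop date will be equal to the start date".

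The dates feed a classification in SAP 7.0: "Prior medication is defined as any medication taken before the date of the first dose of randomized IP". A concomitant medication is one taken on or after that date. Both classes are tabulated by treatment group for the Safety Population.

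For a start date with only the year recorded, where that year is the first-dose year, SAP 13.8.1 says "the month and day of the first dose of IP will be assigned to the missing fields". For a stop date lacking only the day, in a month before the last-dose month, 13.8.2 assigns the last day of the recorded month.

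**The concern.** Two programmers who each follow the SAP can build different medication datasets. Whichever rule runs first makes the two dates equal, so the other never acts, and nothing in the output would show that a choice had been made.

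At stake is how background treatment is described. Investigational product is given on top of local standard of care, and SAP 13.8 applies explicitly to background antidepressant therapy. If a drug recorded as ending before the first dose is moved onto the first-dose date, it enters the concomitant table and also drops out of the prior table. Partial dates are plausible, because Protocol 9.4.9 collects "psychotropic medication history during the previous 2 years" and 12 months of history for other drugs.

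A second defect sits inside the 13.8 rule: it lets an imputed stop date overwrite a start date that the site recorded in full.

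**Working it through.** The plan states no figure to reproduce; the check applies the date rules. All calendar dates below are illustrative assumptions. The rules come from SAP 7.0, 13.8, 13.8.1 and 13.8.2.

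**Step 1. Worked example.** First dose 11 June 2018; last dose 21 days later, 2 July 2018. Start recorded as 2018, stop as May 2018.

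- Start (13.8.1, year-only, first-dose year): 11 June 2018.
- Stop (13.8.2, month before the last-dose month): 31 May 2018.
- 31 May is before 11 June, so both conflict rules are triggered.
- Under 13.8: start = stop = 31 May, before first dose. Prior only.
- Under 13.8.2: start = stop = 11 June, the first-dose date. Concomitant only.

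**Step 2. How many stop months behave this way.** With a year-only start in the first-dose year, the imputed start is the first-dose date. An imputed stop precedes it only if the recorded stop month is earlier in that year than the first-dose month. If the first dose is in calendar month m, that is m − 1 months: January 0, June 5, December 11.

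**Step 3. The other conflict patterns.** For self-consistent records with an incomplete stop, a conflict arises in four patterns of missing fields. The counts are from an enumeration over four assumed first-dose dates, with the last dose 0, 7 or 21 days later. They show which patterns matter and are not expected frequencies.

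| Start | Stop | Conflicts | Class under 13.8 and 13.8.2 |
|---|---|---|---|
| complete | day missing | 1,097 | concomitant under both |
| complete | month and day missing | 3,433 | concomitant under both |
| day missing | month and day missing | 2,068 | concomitant under both |
| month missing | day missing | 25,566 | 15,864 prior under both; 9,702 prior only versus concomitant only |

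In the first three rows the conflicting stop is imputed to the last-dose date, or to the first day of a later month or year. It is never before the first dose, so both rules leave the drug concomitant. In the fourth row, a start year before the first-dose year is imputed to 31 December of that year, so the drug is prior either way: start 2017 and stop May 2017 give 31 December and 31 May 2017. The 9,702 are the Step 1 pattern (25,566 − 15,864 = 9,702), and in all of them the true stop was before the first dose. For these, 13.8 gives the right class and 13.8.2 the wrong one.

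**Step 4. Overwriting a recorded date.** First dose 17 February 2019, last dose 10 March 2019, start recorded in full as 20 March 2019, stop March 2019. The stop is imputed to 10 March. Rule 13.8 then changes the recorded 20 March start to 10 March. Rule 13.8.2 would instead move the stop to 20 March, still inside its recorded month. The class is concomitant under both, but 13.8 has discarded a known date.

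**The case against.** The best case against making much of this is that it is narrow. In three of the four conflict patterns the class never changes, and in the fourth it changes only for a year-only start in the first-dose year. The site must know the month a recent drug stopped but not the month it started. Medication changes after Screening are recorded as they occur (Protocol 9.4.9), so treatment begun during the study should seldom have a year-only start. The same rules apply in both arms, and the output is descriptive. Manual and programmatic checks for completeness and logic (Protocol 9.6.2) should catch records that contradict themselves. All of this stands, and it limits the point to a minor one.

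It does not remove the contradiction. Both sentences are in visible text, share one condition and prescribe opposite actions. Redacted text follows 13.8.2 and could not be checked.

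A reader might infer more: that the conflict generally decides whether drugs count as prior or concomitant, that the two-year history makes the pattern common, or that the treatment comparison is affected. The documents support none of these. The class changes only in the pattern above. A start year before the first-dose year cannot change class, so most of a two-year history is out of reach. No frequency of partial dates is given. The visible primary and key secondary models (SAP 9.1 and 9.2) do not use medication dates.

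**Conclusion.** The contradiction is real and should be corrected, at low priority. As written, the SAP allows a self-consistent record of a drug that ended before dosing to be tabulated as concomitant. This needs a start with no month in the first-dose year and a stop with a known earlier month of that year and no day. Between 0 and 11 stop months are exposed, depending on the calendar month of the first dose; how many patients that means cannot be derived from the documents. Rule 13.8 also permits a recorded start date to be overwritten. The consequences are confined to descriptive Safety Population medication tables. The conclusion assumes that the redacted text sets no precedence between the two rules.

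**What to change.** Put one identical rule in SAP 13.8 and 13.8.2 for an imputed stop date that precedes the start date:

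- If the start date lacks its month, set the start to the imputed stop date.
- If the start month is recorded, with or without the day, keep the start and set the imputed stop date equal to it.

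Send records whose recorded fields contradict each other (for example, start 20 June 2018 and stop May 2018) to query; no imputation rule can respect both entries.

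Deleting one of the present sentences is not enough. Keeping only 13.8.2 leaves the misclassification, and keeping only 13.8 leaves the overwriting of recorded starts. Moving the start whenever any part of it was imputed also fails. With first dose 4 June 2018, last dose 25 June 2018, start July 2018 and stop 2018, the imputed dates are 1 July and 25 June, and that rule would move the start to 25 June, outside its recorded month. The proposed rule keeps 1 July and moves the stop to it. For self-consistent records it alters only fields that were missing.

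Cost: one sentence in each section and minor programming.

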13.8.1 Incomplete Start Date

The following rules will be applied to impute the missing numeric fields for an incomplete prior or concomitant medication start date.

Missing month and day

- If the year of the incomplete start date is the same as the year of the first dose of IP, the month and day of the first dose of IP will be assigned to the missing fields.
- If the year of the incomplete start date is before the year of the first dose of IP, *December 31* will be assigned to the missing fields.
- If the year of the incomplete start date is after the year of the first dose of IP, *January 1* will be assigned to the missing fields.

Missing month only

- If only the month is missing, the day will be treated as missing and both the month and the day will be replaced according to the above procedure.

Missing day only

- If the month and year of the incomplete start date are the same as the month and year of the first dose of IP, the day of the first dose of IP will be assigned to the missing day.
- If either the year of the incomplete start date is before the year of the date of the first dose of IP or if both years are the same, but the month of the incomplete start date is before the month of the date of the first dose of IP, the last day of the month will be assigned to the missing day.
- If either the year of the incomplete start date is after the year of the date of the first dose of IP or if both years are the same, but the month of the incomplete start date is after the month of the date of the first dose of IP, the first day of the month will be assigned to the missing day.

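### SAP 13.8.1 and 13.8.2 ignore what the Visit 1 history already shows, so some partly dated drugs are lost from 'prior' or wrongly counted as 'concomitant' (descriptive tables only)

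*SAP*

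**What the plan says.** SAP 13.8 sets the scope: "For prior or concomitant medications, including background ADT, incomplete (i.e., partially missing) start dates and/or stop dates will be imputed".

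**Starts (SAP 13.8.1).** If month and day are missing and the year is that of the first dose, "the month and day of the first dose of IP will be assigned to the missing fields". If only the day is missing, in the month and year of the first dose, "the day of the first dose of IP will be assigned to the missing day". A missing month alone is handled as if the day were missing too. A start in an earlier year becomes 31 December of that year, and one in an earlier month becomes the last day of that month.

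**Stops (SAP 13.8.2).** The structure is the same, but the reference is the last dose: for a year-only stop in the last-dose year, "the month and day of the last dose of IP will be assigned to the missing fields".

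**Guard (SAP 13.8).** If a complete stop date precedes the imputed start, the start is moved back to the stop date.

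**Classification (SAP 7.0; same definitions in Protocol 9.7.4.1).** One class looks back from dosing: "Prior medication is defined as any medication taken before the date of the first dose of randomized IP". The other class runs from the dosing day onward, and a drug may belong to both: "Concomitant medication is defined as any medication taken on or after the date of the first dose of randomized IP".

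**Source of the records (Protocol 9.4.9).** "Medication history (psychotropic medication history during the previous 2 years and all other medications during the past 12 months) will be recorded at Screening". Later changes and additions are recorded afterwards.

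**The concern.** A drug entered in the Visit 1 history is known to have begun before the first dose. If it was reported there as stopped, it is also known to have ended before the first dose. The imputation rules use neither fact. They look only at whether the known year or month matches that of the first or last dose, and on a match they move the date to the dosing date.

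The investigational product is given on top of local standard of care, with limited restrictions. The prior and concomitant medication tables are therefore a main visible account of the treatment each arm brought in and received. The error also has a direction: affected starts are taken out of prior use, and affected stops are added to concomitant use.

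**Working it through.** The plan states no figure on this point, so there is none to reproduce. The check applies the rules to example records and then sizes the effect under stated assumptions.

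**Step 1: example records.** Assumed first dose 15 May 2019 and last dose 21 days later, 5 June 2019. All drugs truly began before the first dose.

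| Record | Imputed | Classified as | Correct? |
|---|---|---|---|
| Ongoing, start 2019 | start 15 May 2019 | concomitant only | no, prior lost |
| Ongoing, start May 2019 (true 3 May) | start 15 May 2019 | concomitant only | no, prior lost |
| Ongoing, start Feb 2019 | start 28 Feb 2019 | both | yes |
| Ongoing, start 2018 | start 31 Dec 2018 | both | yes |
| Start 2019, complete stop 20 Mar 2019 | start = stop = 20 Mar 2019 | prior only | yes |
| Complete start 2018, stop 2019 (true Mar) | stop 5 June 2019 | both | no, concomitant added |
| Complete start, stop May 2019 (true 8 May) | stop 31 May 2019 | both | no, concomitant added |
| Complete start, stop Mar 2019 | stop 31 Mar 2019 | prior only | yes |
| Start 2019 and stop 2019 | 15 May to 5 June 2019 | concomitant only | no, wrong on both |

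A change of year or month does not rescue the stops. If dosing crosses New Year, a year-only stop in the first-dose year becomes 31 December. If the last dose is in a later month, a day-missing stop in the first-dose month becomes the last day of that month. Both fall on or after the first dose.

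None of these records triggers the separate conflict between 13.8 and 13.8.2 over an imputed stop that precedes the start. One that does is start 2019 with stop Mar 2019. Under 13.8 both dates become 31 March (correct). Under 13.8.2 both become 15 May (wrong on both counts).

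**Step 2: size, starts.** Let m be the length in years of the calendar unit that is known (1 for year-only, 1/12 for day-missing) and L the look-back in years (1 for other drugs, 2 for psychotropics, from Protocol 9.4.9). Assume first-dose dates uniform over the year and starts uniform over the look-back, measured back from the first dose. On average m/2 of the unit has passed at dosing, so the share that loses prior status is m/(2L).

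- Year-only: 1/2 = 0.50 (L = 1); 1/4 = 0.25 (L = 2).
- Day-missing: 1/24 = 0.042 (L = 1); 1/48 = 0.021 (L = 2).

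**Step 3: size, stops.** Assume also that the stop is uniform between the start and the first dose. For a start x years before dosing, the chance that the stop falls in the first-dose unit is 1 − x/(2m) if x ≤ m, and m/(2x) if x > m. Averaging over x from 0 to L gives (m/L) × [0.75 + 0.5 ln(L/m)].

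- Year-only: 0.75 (L = 1); 0.5 × (0.75 + 0.347) = 0.548 (L = 2).
- Day-missing: (1/12) × (0.75 + 1.242) = 0.166 (L = 1); (1/24) × (0.75 + 1.589) = 0.097 (L = 2).

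A simulation in whole days (60,000 draws per scenario, last dose 21 days after the first) gives 0.501 and 0.249, 0.040 and 0.020 for starts, and 0.750 and 0.548, 0.162 and 0.094 for stops. The small differences in the day-missing rows come from counting whole days. Each share is of partial dates of that type, not of all medication records.

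**The case against.** The strongest case on the other side is that little depends on this.

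- **Efficacy.** The visible models (SAP 9.1 and 9.2) contain no medication term, so no visible estimate or p-value changes. This stands.
- **Other displays.** An ongoing antidepressant still counts as concomitant, and SAP 7.0 separately summarizes previous psychotropic treatment by arm. This stands.
- **Convention.** The start rule matches the adverse-event rule in SAP 13.7. This does not rescue it. For an event of unknown timing, choosing the first-dose date is cautious. For a Visit 1 history drug, the timing relative to dosing is already known.
- **Unseen text.** Part of the SAP after 13.8.2 is redacted, and the table specifications are in a separate document, so handling there cannot be excluded. No visible text corrects the rules.

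Three stronger readings are tempting and not supported. A reader might infer that background antidepressants in general drop out of the prior table; only starts that are year-only in the first-dose year, or day-missing in the first-dose month, do so. A reader might infer that the tables cannot show whether background treatment was balanced around Day 1. But the concomitant definition covers any use on or after the first dose, so even complete dates would not make it a Day 1 display, and the same rules apply to both arms. A reader might also take the share of day-missing starts affected as about 49%. That holds only for starts in the 30 days before dosing; over the full look-back it is 0.49 × 30/365 = 4%, or 0.49 × 30/730 = 2%.

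**Conclusion.** The concern holds in a limited form. As written, the rules give wrong prior or concomitant counts for Visit 1 history drugs whose partial date falls in the first-dose year or month. For ongoing drugs the error is loss from prior. For drugs stopped before dosing it is a false concomitant count, joined by loss from prior when the start is also partial in that year or month. The first error comes from 13.8.1 and the second mainly from the last-dose anchor in 13.8.2.

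The size rests on the uniform-date assumptions and on the share of partial dates, which the documents do not give. The stop figures in particular depend on where stops are placed within the look-back, and drugs started before the look-back would mostly keep their prior status. The total effect could be negligible if few dates are partial. The tables can misstate background therapy, but they are descriptive. Severity is minor.

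**What to change.** In SAP 13.8.1, add that for any drug recorded as history at Visit 1, the imputed start may not be later than the day before the first dose. In SAP 13.8.2, add that for any drug recorded at Visit 1 as already stopped, the imputed stop may not be later than the day before the first dose. Keep the current rules for drugs first recorded after Visit 1. With these caps every record in the table above is classified correctly.

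The cap should be the day before the first dose, not the Visit 1 date. Protocol 9.1.2 allows Baseline within 1 day of Screening, so the two dates may coincide, and a stop capped at Visit 1 would then still count as concomitant.

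The conflict between 13.8 and 13.8.2 over a stop that precedes the start should be reconciled in the same edit.

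The cost is one sentence in each subsection and a few lines of programming. One thing must be confirmed first: Protocol 9.4.9 shows that the history is recorded at Visit 1, but not that the eCRF holds a separate ongoing or stopped status.
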